4. STUDY DESIGN

4.1. Study Design

This is a Phase 3b, multicenter, double-blind, parallel group, randomized, study that will evaluate the efficacy and safety of 2 treatment regimens of edaravone for a period of 48 weeks in subjects with ALS as follows:

- Group 1: Edaravone 105 mg oral dose once daily for 48 weeks
- Group 2: Edaravone 105 mg oral dose in for 14 days, followed by a 14-day placebo. Subsequently, repeat edaravone 105 mg oral dose in for 10 days followed by 18-day placebo (regimen denoted as on/off).

Eligible subjects will be randomized at baseline in a 1:1 ratio to receive 1 of 2 treatment groups. Randomization will be stratified according to ALSFRS-R rate of decline score for 8 weeks screening period (2 levels strata of -1,-2 or -3,-4) and geographical region (3 levels strata of Europe, America or Asia Pacific).

Concomitant use of riluzole is permitted when the doses and regimens will remain unchanged from the day of evaluation of ALSFRS-R at the screening visit, through the end-of-treatment (EOT) or early termination (ET). Although dose reduction, dose interruption or discontinuation due to the onset of AEs, progression of dysphagia, or gastrostomy while on oral edaravone 105 mg are allowed, it is prohibited to initiate the use of riluzole. Subjects who initiate riluzole therapy de-novo during the treatment period will be discontinued from the study. The use of AMX0035 will be allowed for patients in the event that it becomes commercially available via prescription in their respective country. AMX0035 should be taken at least 1 hour after MT-1186.

This study consists of a screening period of 8 weeks, a double blind treatment period of 48 weeks, and a safety follow-up period of 2 weeks. A schedule of assessment of all study procedures is provided in Table 1.

- **Screening period:** Screening assessments will be performed up to 8 weeks (\pm 7 days) prior to Day 1. All screening evaluations must be completed and reviewed to confirm that potential subjects meet all eligibility criteria. If a subject has not met all eligibility criteria at the end of the screening period, the subject will be registered as a screen fail. Screen fail subjects may be eligible for re-screening 1 time.
- **Double-blind Treatment Period:** Subjects who successfully complete the screening period will return to the study clinic on Day 1 in a fasting state (eg, without breakfast) and inclusion

Statistical Analysis Plan
Protocol No. MT-1186-A02

Visit	1	2	3	4	5	6	7	8	9	10	11	12	13
Informed consent	X												14
Eligibility criteria	X	X											
Demographics ^d	X												
Medical history/diagnosis ^d	X												
Prior medications	X	X											
Vital signs ^e	X	X		X	X		X		X		X		X
Pregnancy test (WOCP only)	X	X					X						X
Full physical examination ^f	X												X
Routine physical examination ⁱ		X		X	X		X		X		X		
12-lead ECG ^g	X	X						X					X
Body weight	X	X		X	X		X		X		X		X
Height	X												
Randomization	X												
ALSFRS-R	X	X		X	X		X		X		X		X
ALSAQ0	X								X		X		X
C-SSRS	X	X					X		X		X		X
CAFS ^h		X							X		X		X

Statistical Analysis Plan
Protocol No. MT-1; 36-A02

Mitsubishi Tanabe Pharma America, Inc.

ASSESSMENT	Screening Period		Double-Blind Treatment Period										Safety Follow-up Period	
	Screening In-clinic visit	Baseline In-clinic visit	Telephone visit	In-clinic visit	In-clinic visit	Telephone visits	In-clinic visit	Telephone visits	In-clinic visit	Telephone visits	In-clinic visit	EOT/ET Period	EOS ^b Telephone visit	
Week (window)	-8 (= 7D)	Day 1 (= 3D)	2 (= 3D) ^c	4 (= 3D) ^c	8 (= 3D) ^c	12 (= 3D) ^c	16 (= 3D) ^c	20 (= 3D) ^c	24 (= 3D) ^c	28 (= 3D) ^c	32 (= 3D) ^c	36 (= 3D) ^c	40 (= 3D) ^c	44 (= 3D) ^c
Day	-56	1	15	29	57	85	113	141	169	197	225	253	281	309
Cycle		1		2	3	4	5	6	7	8	9	10	11	12
Visit	1	2	3	4	5	6	7	8	9	10	11	12	13	14
%FVC	X	X												
%SVC	X	X	X	X	X	X	X	X	X	X	X	X	X	X
Time to event ^d		X	X	X	X	X	X	X	X	X	X	X	X	X
Biomarker(s)		X		X		X		X		X		X		X
Optional biomarkers		X		X		X		X		X		X		X
Nerve conduction test ^e		X			X		X		X		X		X	
Hematology ^f	X	X		X	X	X	X	X	X	X	X	X	X	X
Chemistry ^g	X	X		X	X	X	X	X	X	X	X	X	X	X
Vitamin B6	X	X		X	X	X	X	X	X	X	X	X	X	X
Urinalysis ^h	X	X		X	X	X	X	X	X	X	X	X	X	X
PK sample ⁱ	X		X		X		X		X		X		X	
PG sample ^j														
Edaravone/Placebo ^k														
Dispense Study Drug		X		X	X	X	X	X	X	X	X	X	X	X
Unsteadiness and sensory evaluation ^l	X	X		X	X	X	X	X	X	X	X	X	X	X
Adverse events	X	X		X	X	X	X	X	X	X	X	X	X	X
Concomitant medications	X	X		X	X	X	X	X	X	X	X	X	X	X
Dispense e-diary	X													
Review e-diary			X	X	X					X		X		
Collect e-diary												X		

Statistical Analysis Plan
Protocol No. MT-1186-A02

Mitsubishi Tanabe Pharma America, Inc.

Abbreviation: ALSFRS-R = Amyotrophic Lateral Sclerosis functional rating scale- revised; ALSAQ = Amyotrophic Lateral Sclerosis Assessment Questionnaire; CAFS = Combined Assessment of Function and Survival; C-SSRS = Columbia-Suicide Severity Rating Scale; D = Day; ECG = Electrocardiogram; FVC = Force vital capacity; EOS = End-of-study; EOT = End-of-treatment; $\geq \Gamma$ = early termination; PG = pharmacogenomic; PK = pharmacokinetic; SVC = Slow Vital Capacity; WOCP = Women of Childbearing Potential.

- a. For subjects who decide to enroll into the extension study, the Week 48 study procedures will be used as the screening/entry criteria. Subjects who withdraw from the study will complete the procedures listed in Visit 15. If study treatment is discontinued, study sites must follow-up with phone calls at Weeks 24, 36, and 48 per the Schedule of Activities.
- b. For subjects who complete the double-blind treatment period and who do not enroll into the extension study, a safety follow-up telephone visit will be conducted. If a subject enrolls into the extension study, a safety follow-up telephone visit does not need to be conducted.
- c. Demographics will include age, sex, race, and ethnicity.
- d. Medical/surgical history including any medical condition or surgical history prior to the screening visit.
- e. Vital signs will include sitting systolic and diastolic blood pressure, orthostatic hypotension, heart rate, respiratory rate, and axillary, oral, temporal (skin-based), or tympanic body temperature (same method to be used throughout).
- f. Physical examination:
 1. A full physical examination will consist of an assessment of major body parts and systems: abdominal, cardiovascular, general appearance, head, eyes, ears/nose/throat, lymph nodes, musculoskeletal, neck, neurological, dermatological, respiratory, and 'other'.
 2. A routine physical examination will occur at all clinic visits except at the screening and EOT/ET. It will consist of an assessment of the following body systems:
 - abdominal, cardiovascular, general appearance, respiratory, neurological, and other.
- g. A 12-lead ECG will be performed after the subject has rested for at least 5 minutes in a supine position. The ECG must include the following measurements: R wave to R wave interval, heart rate, QRS, QT, QTcB, and QTcF. The Investigator will perform an overall evaluation of the ECG for safety purposes and the recording will be reported as 'normal', 'abnormal clinically significant (CS)', or 'abnormal not clinically significant (NCS)'. Abnormalities of clinical significance will be reported as AEs. Repeat measurements will be performed¹ if needed.
- h. To be calculated by the Sponsor.
 - i. Events are time to death, tracheostomy, or permanent assisted mechanical ventilation (≥ 23 hours/day). If subject discontinues treatment, sites must follow-up with phone calls at Weeks 24, 36, and 48.
 - j. Will be drawn at the same times as the biomarkers. The additional biomarkers sampling will be performed at selected study sites where local regulations and IECs allow.
 - k. At selected sites, Investigator (or Sub-I) will measure the parameters Compound Muscle Action Potential (CMAP), Motor Unit Number Index (MUNIX), Sensory Nerve Action Potential (SNAP), and Sensory Nerve Conduction Velocity (SNCV).

Statistical Analysis Plan
Protocol No. MTT-1186-A02

1. To include: red blood cell count, hemoglobin, hematocrit value, white blood cell (WBC) count with differential, and platelet count.
2. To include: albumin, total protein, aspartate aminotransferase (AST), alanine aminotransferase (ALT), lactate dehydrogenase (LDH), alkaline phosphatase (ALP), c-reactive protein, total bilirubin, direct bilirubin, creatine kinase (CK), total cholesterol, triglycerides, blood urea nitrogen (BUN), bicarbonate, serum glucose, serum creatinine level, uric acid, sodium (Na), potassium (K), chloride, calcium (Ca) and cystatin C.
3. To include protein, glucose, occult blood, WBCs, urobilinogen, and bilirubin.
4. The PK sampling will be performed at selected study sites, and blood samples will be taken from subjects at the following time points: Day 1: 15, 30 minutes, and 1 hour post-dose. One sample at each of the visits for Weeks 4 and 12 after dosing. For PK samples collected at Weeks 4 and 12, subjects will receive their daily dose of cycle 2 (Week 4) and cycle 4 (Week 12) in clinic, on an empty stomach, and PK samples will be collected at least 2 hours post-dose, following an overnight fast. Visit window for subjects who participate in PK collection during Week 4 and Week 12 will be restricted to +3 days.
5. The PG sampling will be performed at selected study sites where local regulations and IECs allow and will be collected 1 time, post-dose any time at Visits 2 through 15.
6. Subjects will receive oral edaravone 105 mg once daily in Cycles 1-12, or oral edaravone 105 mg administered for 14 days, followed by placebo for 14 days in Cycle 1, and then oral edaravone 105 mg administered for 10 days, followed by placebo for 18 days (regimen denoted as on/off) in Cycles 2 through 12, following an overnight fast and subjects must continue to fast at least 1 to 2 hours post-dose before the next meal (eg, breakfast).
7. Assessment of unsteadiness and peripheral sensation will be evaluated by interview and assessment of vibratory sensation with a tuning fork applied to the lateral side of the right and left ankles. Abnormalities of clinical significance will be reported as AEs.

Mitsubishi Tanabe Pharma America, Inc.

Country specific protocol for Japan

ASSESSMENT ^a	Screening Period ^a		Double-Blind Treatment Period ^a										EOT/ET ^a Period ^a		Safety Follow-up Period ^a		
	Screening ^a In-clinic visit ^a	Baseline ^a In-clinic visit ^a	In-clinic visit ^a	In-clinic visit ^a	In-clinic visit ^a	In-clinic visit ^a	In-clinic visit ^a	In-clinic visit ^a	In-clinic visit ^a	In-clinic visit ^a	In-clinic visit ^a	In-clinic visit ^a	In-clinic visit ^a	In-clinic visit ^a	In-clinic visit ^a		
Week (window) ^a	-8 ^a (± 7D) ^a	Day 1 ^a (± 2D) ^a	Day 8 ^a (± 3D) ^a	Day 2 ^a (± 3D) ^a	4 ^a (± 3D) ^a	8 ^a (± 3D) ^a	12 ^a (± 3D) ^a	16 ^a (± 5D) ^a	20 ^a (± 5D) ^a	24 ^a (± 5D) ^a	28 ^a (± 5D) ^a	32 ^a (± 5D) ^a	36 ^a (± 5D) ^a	40 ^a (± 5D) ^a	44 ^a (± 5D) ^a	48 ^a (-7D) ^a	50 ^a (-5D) ^a
Day	-56 ^a -2 ^a	1 ^a	8 ^a	15 ^a	29 ^a	57 ^a	85 ^a	113 ^a	141 ^a	169 ^a	197 ^a	225 ^a	253 ^a	281 ^a	309 ^a	337 ^a	351 ^a
Cycle ^a	1 ^a	1 ^a	2 ^a	2 ^a	3 ^a	4 ^a	5 ^a	6 ^a	7 ^a	8 ^a	9 ^a	10 ^a	11 ^a	12 ^a	13 ^a	14 ^a	15 ^a
Visit ^a	1 ^a	2 ^a	V2D8 ^a	3 ^a	4 ^a	5 ^a	6 ^a	7 ^a	8 ^a	9 ^a	10 ^a	11 ^a	12 ^a	13 ^a	14 ^a	15 ^a	16 ^a
Informed consent ^a	X ^a	X ^a	X ^a	X ^a	X ^a	X ^a	X ^a	X ^a	X ^a	X ^a	X ^a	X ^a	X ^a	X ^a	X ^a	X ^a	X ^a
Eligibility criteria ^a	X ^a	X ^a	X ^a	X ^a	X ^a	X ^a	X ^a	X ^a	X ^a	X ^a	X ^a	X ^a	X ^a	X ^a	X ^a	X ^a	X ^a
Demographics ^a	X ^a	X ^a	X ^a	X ^a	X ^a	X ^a	X ^a	X ^a	X ^a	X ^a	X ^a	X ^a	X ^a	X ^a	X ^a	X ^a	X ^a
Medical history/diagnosis ^a	X ^a	X ^a	X ^a	X ^a	X ^a	X ^a	X ^a	X ^a	X ^a	X ^a	X ^a	X ^a	X ^a	X ^a	X ^a	X ^a	X ^a
Prior medications ^a	X ^a	X ^a	X ^a	X ^a	X ^a	X ^a	X ^a	X ^a	X ^a	X ^a	X ^a	X ^a	X ^a	X ^a	X ^a	X ^a	X ^a
Vital signs ^a	X ^a	X ^a	X ^a	X ^a	X ^a	X ^a	X ^a	X ^a	X ^a	X ^a	X ^a	X ^a	X ^a	X ^a	X ^a	X ^a	X ^a
Pregnancy test (WoCP only) ^a	X ^a	X ^a	X ^a	X ^a	X ^a	X ^a	X ^a	X ^a	X ^a	X ^a	X ^a	X ^a	X ^a	X ^a	X ^a	X ^a	X ^a
Full physical examination ^a	X ^a	X ^a	X ^a	X ^a	X ^a	X ^a	X ^a	X ^a	X ^a	X ^a	X ^a	X ^a	X ^a	X ^a	X ^a	X ^a	X ^a
Routine physical examination ^a	X ^a	X ^a	X ^a	X ^a	X ^a	X ^a	X ^a	X ^a	X ^a	X ^a	X ^a	X ^a	X ^a	X ^a	X ^a	X ^a	X ^a
12-lead ECG ^a	X ^a	X ^a	X ^a	X ^a	X ^a	X ^a	X ^a	X ^a	X ^a	X ^a	X ^a	X ^a	X ^a	X ^a	X ^a	X ^a	X ^a
Body weight ^a	X ^a	X ^a	X ^a	X ^a	X ^a	X ^a	X ^a	X ^a	X ^a	X ^a	X ^a	X ^a	X ^a	X ^a	X ^a	X ^a	X ^a
Height ^a	X ^a	X ^a	X ^a	X ^a	X ^a	X ^a	X ^a	X ^a	X ^a	X ^a	X ^a	X ^a	X ^a	X ^a	X ^a	X ^a	X ^a
Randomization ^a	X ^a	X ^a	X ^a	X ^a	X ^a	X ^a	X ^a	X ^a	X ^a	X ^a	X ^a	X ^a	X ^a	X ^a	X ^a	X ^a	X ^a
AL-SFRS-R ^a	X ^a	X ^a	X ^a	X ^a	X ^a	X ^a	X ^a	X ^a	X ^a	X ^a	X ^a	X ^a	X ^a	X ^a	X ^a	X ^a	X ^a
AL-SAQ0 ^a	X ^a	X ^a	X ^a	X ^a	X ^a	X ^a	X ^a	X ^a	X ^a	X ^a	X ^a	X ^a	X ^a	X ^a	X ^a	X ^a	X ^a
C-SRS ^a	X ^a	X ^a	X ^a	X ^a	X ^a	X ^a	X ^a	X ^a	X ^a	X ^a	X ^a	X ^a	X ^a	X ^a	X ^a	X ^a	X ^a

Statistical Analysis Plan
Protocol No. MT-1186-A02

Mitsubishi Tanabe Pharma America, Inc.

ASSESSMENT ^a	Screening Period ^a		Double-Blind Treatment Period ^a												EO/I/ET ^a Period ^a		Safety Follow-up Period ^a	
	Screening Baseline ^a In-clinic visit ^a	Screening Day 1 ^a In-clinic visit ^a	In-clinic visit ^a	In-clinic visit ^a	In-clinic visit ^a	In-clinic visit ^a	In-clinic visit ^a	In-clinic visit ^a	In-clinic visit ^a	In-clinic visit ^a	In-clinic visit ^a	In-clinic visit ^a	In-clinic visit ^a	In-clinic visit ^a	In-clinic visit ^a	EO/I/ET ^a In-clinic visit ^a	EO/I/ET ^a In-clinic visit ^a	
Week (window) ^a	-8 ^a (± 7D) ^a	Day 8 ^a (± 2D) ^a	2 ^a (± 3D) ^a	4 ^a (± 3D) ^a	8 ^a (± 3D) ^a	12 ^a (± 5D) ^a	16 ^a (± 5D) ^a	20 ^a (± 5D) ^a	24 ^a (± 5D) ^a	28 ^a (± 5D) ^a	32 ^a (± 5D) ^a	36 ^a (± 5D) ^a	40 ^a (± 5D) ^a	44 ^a (± 5D) ^a	48 ^a (± 5D) ^a	50 ^a (± 5D) ^a		
Day	-5 ^a 1 ^a	1 ^a 8 ^a	15 ^a 29 ^a	57 ^a 2 ^a	85 ^a 3 ^a	113 ^a 4 ^a	141 ^a 5 ^a	169 ^a 6 ^a	197 ^a 7 ^a	225 ^a 8 ^a	253 ^a 9 ^a	281 ^a 10 ^a	309 ^a 11 ^a	337 ^a 12 ^a	351 ^a 12 ^a			
Cycle ^a	1 ^a	1 ^a	2 ^a	2 ^a	3 ^a	4 ^a	5 ^a	6 ^a	7 ^a	8 ^a	9 ^a	10 ^a	11 ^a	12 ^a	12 ^a			
Visit ^a	2 ^a	2 ^a	2 ^a	2 ^a	2 ^a	2 ^a	2 ^a	2 ^a	2 ^a	2 ^a	2 ^a	2 ^a	2 ^a	2 ^a	2 ^a			
CAFS ^a	X ^a	X ^a	X ^a	X ^a	X ^a	X ^a	X ^a	X ^a	X ^a	X ^a	X ^a	X ^a	X ^a	X ^a	X ^a			
%FVC ^a	X ^a	X ^a	X ^a	X ^a	X ^a	X ^a	X ^a	X ^a	X ^a	X ^a	X ^a	X ^a	X ^a	X ^a	X ^a			
%SVC ^a	X ^a	X ^a	X ^a	X ^a	X ^a	X ^a	X ^a	X ^a	X ^a	X ^a	X ^a	X ^a	X ^a	X ^a	X ^a			
Time to event ^a	2 ^a	2 ^a	2 ^a	2 ^a	2 ^a	2 ^a	2 ^a	2 ^a	2 ^a	2 ^a	2 ^a	2 ^a	2 ^a	2 ^a	2 ^a			
Biomarker(s) ^a	X ^a	X ^a	X ^a	X ^a	X ^a	X ^a	X ^a	X ^a	X ^a	X ^a	X ^a	X ^a	X ^a	X ^a	X ^a			
Optional biomarkers ^a	X ^a	X ^a	X ^a	X ^a	X ^a	X ^a	X ^a	X ^a	X ^a	X ^a	X ^a	X ^a	X ^a	X ^a	X ^a			
Nerve conduction test ^a	X ^a	X ^a	X ^a	X ^a	X ^a	X ^a	X ^a	X ^a	X ^a	X ^a	X ^a	X ^a	X ^a	X ^a	X ^a			
Hematology ^a	X ^a	X ^a	X ^a	X ^a	X ^a	X ^a	X ^a	X ^a	X ^a	X ^a	X ^a	X ^a	X ^a	X ^a	X ^a			
Chemistry ^a	X ^a	X ^a	X ^a	X ^a	X ^a	X ^a	X ^a	X ^a	X ^a	X ^a	X ^a	X ^a	X ^a	X ^a	X ^a			
Vitamin B6 ^a	X ^a	X ^a	X ^a	X ^a	X ^a	X ^a	X ^a	X ^a	X ^a	X ^a	X ^a	X ^a	X ^a	X ^a	X ^a			
Urinalysis ^a	X ^a	X ^a	X ^a	X ^a	X ^a	X ^a	X ^a	X ^a	X ^a	X ^a	X ^a	X ^a	X ^a	X ^a	X ^a			
PK sample ^a	X ^a	X ^a	X ^a	X ^a	X ^a	X ^a	X ^a	X ^a	X ^a	X ^a	X ^a	X ^a	X ^a	X ^a	X ^a			
PG samples ^a	2 ^a	2 ^a	2 ^a	2 ^a	2 ^a	2 ^a	2 ^a	2 ^a	2 ^a	2 ^a	2 ^a	2 ^a	2 ^a	2 ^a	2 ^a			
Edaravone/Placebo ^a	2 ^a	2 ^a	2 ^a	2 ^a	2 ^a	2 ^a	2 ^a	2 ^a	2 ^a	2 ^a	2 ^a	2 ^a	2 ^a	2 ^a	2 ^a			
Dispense Study Drug ^a	X ^a	X ^a	X ^a	X ^a	X ^a	X ^a	X ^a	X ^a	X ^a	X ^a	X ^a	X ^a	X ^a	X ^a	X ^a			
Unsteadiness and sensory evaluation ^a	X ^a	X ^a	X ^a	X ^a	X ^a	X ^a	X ^a	X ^a	X ^a	X ^a	X ^a	X ^a	X ^a	X ^a	X ^a			
Adverse events ^a	X ^a	X ^a	X ^a	X ^a	X ^a	X ^a	X ^a	X ^a	X ^a	X ^a	X ^a	X ^a	X ^a	X ^a	X ^a			
Concomitant medications ^a	X ^a	X ^a	X ^a	X ^a	X ^a	X ^a	X ^a	X ^a	X ^a	X ^a	X ^a	X ^a	X ^a	X ^a	X ^a			

Statistical Analysis Plan
Protocol No. MT-1186-A02

Mitsubishi Tanabe Pharma America, Inc.

ASSESSMENT ^a	Screening Period ^a		Double-Blind Treatment Period ^a										EOT/ET ^a Period ^a		Safety Follow-up Period ^a		
	Screening ^a In-clinic visit ^a	Baseline ^a In-clinic visit ^a	In-clinic visit ^a	In-clinic visit ^a	In-clinic visit ^a	In-clinic visit ^a	In-clinic visit ^a	In-clinic visit ^a	In-clinic visit ^a	In-clinic visit ^a	In-clinic visit ^a	In-clinic visit ^a	In-clinic visit ^a	In-clinic visit ^a	Telephone visit or In-clinic visit ^a	Telephone visit or In-clinic visit ^a	Telephone visit or In-clinic visit ^a
Week (window) ^a	-8 ^a (\pm 7D) ^a	Day 1 ^a (\pm 2D) ^a	Day 8 ^a (\pm 2D) ^a	2 ^a (\pm 3D) ^a	4 ^a (\pm 3D) ^a	8 ^a (\pm 3D) ^a	12 ^a (\pm 3D) ^a	16 ^a (\pm 5D) ^a	20 ^a (\pm 5D) ^a	24 ^a (\pm 5D) ^a	28 ^a (\pm 5D) ^a	32 ^a (\pm 5D) ^a	36 ^a (\pm 5D) ^a	40 ^a (\pm 5D) ^a	44 ^a (\pm 5D) ^a	48 ^a (\pm 5D) ^a	50 ^a (\pm 5D) ^a
Day	-56 ^a	1 ^a	8 ^a	15 ^a	29 ^a	57 ^a	85 ^a	113 ^a	141 ^a	169 ^a	197 ^a	225 ^a	253 ^a	281 ^a	309 ^a	337 ^a	351 ^a
Cycle ^a	1 ^a	1 ^a	2 ^a	2 ^a	3 ^a	4 ^a	5 ^a	6 ^a	7 ^a	8 ^a	9 ^a	10 ^a	11 ^a	12 ^a	13 ^a	14 ^a	
Visit ^a	1 ^a	2 ^a	V2D8 ^a	3 ^a	4 ^a	5 ^a	6 ^a	7 ^a	8 ^a	9 ^a	10 ^a	11 ^a	12 ^a	13 ^a	14 ^a	15 ^a	16 ^a
Dispense e-diary ^a	1 ^a	X ^a	2 ^a	2 ^a	2 ^a	2 ^a	2 ^a	2 ^a	2 ^a	2 ^a	2 ^a	2 ^a	2 ^a	2 ^a	2 ^a	2 ^a	
Review e-diary ^a	2 ^a	2 ^a	X ^a	2 ^a	X ^a	X ^a	X ^a	X ^a	X ^a	X ^a	X ^a	X ^a	X ^a	X ^a	X ^a	X ^a	
Collect e-diary ^a	2 ^a	2 ^a	2 ^a	2 ^a	2 ^a	2 ^a	2 ^a	2 ^a	2 ^a	2 ^a	2 ^a	2 ^a	2 ^a	2 ^a	2 ^a	2 ^a	

Abbreviation: ALSFRS-R = Amyotrophic Lateral Sclerosis functional rating scale-revised; ALSAQ40 = Amyotrophic Lateral Sclerosis Assessment Questionnaire 40; CAFS = Combined Assessment of Function and Survival; C-SSRS = Columbia-Suicide Severity Rating Scale; D = Day; ECG = Electrocardiogram; FVC = Force vital capacity; EOS = End-of-study; EOT = End-of-treatment; ET = early termination; PG = pharmacogenomic; PK = pharmacokinetic; SVC = Slow Vital Capacity; WOCP = Women of Childbearing Potential.

- For subjects who decide to enroll into the extension study, the Week 48 study procedures will be used as the screening/entry criteria. Subjects who withdraw from the study will complete the procedures listed in Visit 15. If study treatment is discontinued, study sites must follow-up with phone calls at Weeks 24, 36, and 48 per the Schedule of Activities.
- For subjects who complete the double-blind treatment period and who do not enroll into the extension study, a safety follow-up telephone visit will be conducted.
- Demographics will include age, sex, race, and ethnicity.
- Medical/surgical history including any medical condition or surgical history prior to the screening visit.
- Vital signs will include sitting systolic and diastolic blood pressure, orthostatic hypotension, heart rate, respiratory rate, and axillary, oral or tympanic body temperature (same method to be used throughout).
- Physical examination:
 - A full physical examination will consist of an assessment of major body parts and systems: abdominal, cardiovascular, general appearance, head, eyes, ears/nose/throat,

Statistical Analysis Plan
Protocol No. MT-1186-A02

Mitsubishi Tanabe Pharma America, Inc.
lymph nodes, musculoskeletal, neck, neurological, dermatological, respiratory, and 'other'.

2. A routine physical examination will occur at all clinic visits except at the screening and EOT/ET. It will consist of an assessment of the following body systems:
 - abdominal, cardiovascular, general appearance, respiratory, neurological, and other.
 - A 12-lead ECG will be performed after the subject has rested for at least 5 minutes in a supine position. The ECG must include the following measurements: R wave to R wave interval, heart rate, QRS, QT, QTcB, and QTcF. The Investigator will perform an overall evaluation of the ECG for safety purposes and the recording will be reported as 'normal', 'abnormal', 'clinically significant (CS)', or 'abnormal not clinically significant (NCS)'. Abnormalities of clinical significance will be reported as AEs. Repeat measurements will be performed if needed.
 - To be calculated by the Sponsor.
 - Events are time to death, tracheostomy, or permanent assisted mechanical ventilation (≥ 23 hours/day). If subject discontinues treatment, sites must follow-up with phone calls at Weeks 24, 36, and 48.
 - Will be drawn at the same times as the biomarkers. The additional biomarkers sampling will be performed at selected study sites where local regulations and IECs allow.
 - At selected sites, Investigator (or Sub-I) will measure the parameters Compound Muscle Action Potential (CMAP), Motor Unit Number Index (MUNIX), Sensory Nerve Action Potential (SNAP), and Sensory Nerve Conduction Velocity (SNCV).
 - To include: red blood cell count, hemoglobin, hematocrit value, white blood cell (WBC) count with differential, and platelet count.
 - To include: albumin, total protein, aspartate aminotransferase (AST), alanine aminotransferase (ALT), lactate dehydrogenase (LDH), alkaline phosphatase (ALP), gamma-glutamyl transferase (GGT), c-reactive protein, total bilirubin, direct bilirubin, creatine kinase (CK), total cholesterol, triglycerides, blood urea nitrogen (BUN), bicarbonate, serum glucose, serum creatinine level, uric acid, sodium (Na), potassium (K), chloride, calcium (Ca) and cystatin C.
 - To include protein, glucose, occult blood, WBCs, urobilinogen, and bilirubin.
 - The PK sampling will be performed at selected study sites, and blood samples will be taken from subjects at the following time points: Day 1: 15, 30 minutes, and 1 hour post-dose. One sample at each of the visits for Weeks 4 and 12 after dosing. For PK samples collected at Weeks 4 and 12, subjects will receive their daily dose of cycle 2 (Week 4) and cycle 4 (Week 12) at home, on an empty stomach, and PK samples will be collected at least 2 hours post-dose. Visit window for subjects who participate in PK collection during Week 4 and Week 12 will be restricted to +3 days.
 - The PG sampling will be performed at selected study sites where local regulations and IECs allow and will be collected 1 time, post-dose any time at Visits 2 through 15.
 - Subjects will receive oral edaravone 105 mg once daily in Cycles 1-12, or oral edaravone 105 mg administered for 14 days, followed by placebo for 14 days in Cycle 1, and then oral edaravone 105 mg administered for 10 days, followed by placebo for 18 days (regimen denoted as on/off) in Cycles 2 through 12, following an overnight fast and subjects must continue to fast at least 1 to 2 hours post-dose before the next meal (eg, breakfast).

Statistical Analysis Plan
Protocol No. MT-1186-A02

r. Assessment of unsteadiness and peripheral sensation will be evaluated by interview and assessment of vibratory sensation with a tuning fork applied to the lateral side of the right and left ankles. Abnormalities of clinical significance will be reported as AEs.

Mitsubishi Tanabe Pharma America, Inc.

Assessment of unsteadiness and peripheral sensation will be evaluated by interview and assessment of vibratory sensation with a tuning fork applied to the lateral side of the right and left ankles. Abnormalities of clinical significance will be reported as AEs.

4.2. Sample Size and Power Considerations

Assuming the use of a t-test, a 2-sided alpha level of 5% and a 30% dropout rate up to Week 48, a sample size of 190 subjects per groups (380 subjects in total) will provide 85.5% power to detect an effect size of 0.37 (ie, an absolute treatment difference of 2.6 with an associated standard deviation [SD] of 7) in the change from baseline in ALSFRS-R score to Week 48 between edaravone 105 mg oral dose once daily versus edaravone 105 mg oral dose on/off regimen; see details in Appendix 1.

A sample size of 190 subjects per groups will have 78% power to detect statistically significant result for the time to death, tracheostomy, or permanent assisted mechanical ventilation. This calculation assumed a true hazard ratio between edaravone 105 mg daily (test) to edaravone 105 mg on/off regimen (control) of $HR=0.3$. Namely, 70% reduction in the hazard assuming 90% survival rate at Week 48 for the control group. This calculation assumes 2-sided alpha of 5% using the log-rank test and follow-up time of 48 weeks.

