3.2. Study Estimands

3.2.1. Primary Estimand

As pre-defined in the protocol (V5.0), if more than a few death events ($\geq 5\%$ death percentage for all randomized subjects, e.g., ≥ 19 death events) are observed in this study, an alternative primary estimand as well as primary endpoint will be used to incorporate death cases as Intercurrent Events (ICE). It was confirmed that the threshold of 19 death cases was crossed in the blinded data review meeting and therefore, the following back-up estimand will be used with CAFS being the primary endpoint.

The primary estimand construction elements are:

- Treatment of interest: The initially randomized treatment – Group 1 edaravone daily to be compared with Group 2 edaravone on/off during 48-week period.
- Population: Subjects with ALS as defined in the analysis set.
- Variable: CAFS score at Week 48.
- ICEs handling strategy
 - ICE1 – Additional/new AMX0035 treatment during the 48-week double-blind treatment period will be handled using treatment policy strategy.
 - ICE2 – Early discontinuation during the 48-week double-blind treatment period will be handled using hypothetical strategy.
 - ICE3 – Death will be handled within CAFS score derivation using composite variable strategy.
- Population-level summary: Mean difference in the variable (as specified above) between the 2 randomized groups – Group 1 edaravone daily vs Group 2 edaravone on/off.

The treatment effect will be attributed regardless of the use of additional/new AMX0035 treatment (ICE1) and as if early discontinuation events did not occur (ICE2), accounting for Death event (ICE3).

Note: If death after early discontinuation (ICE2) was occurred, the death event will be included.

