3.3. Study Endpoints

3.3.1. Primary Endpoints

The primary efficacy endpoint is CAFS score at Week 48.

3.3.2. Key Secondary Efficacy Endpoints:

The following efficacy endpoints are defined as 'key' secondary and will be controlled for the familywise type I error:

- Change from baseline in % slow vital capacity (SVC) at Week 48
- Change from baseline in Amyotrophic Lateral Sclerosis Assessment Questionnaire (ALSAQ)40 at Week 48
- Time to death, tracheostomy or permanent assisted mechanical ventilation (\geq 23 hours/day)
- Time to death or permanent assisted mechanical ventilation (\geq 23 hours/day)
- Time to death

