3.3.3. Other Secondary Endpoints

The following efficacy endpoints are defined as 'other' secondary:

- Change from baseline in ALS Functional Rating Scale-Revised (ALSFRS-R) score at Weeks 4, 8, 12, 24, 36, and 48
- Change from screening and baseline in % forced vital capacity (FVC) at Weeks 24 and 48
- Change from baseline in %SVC at Weeks 4, 8, 12, 24, and 36
- Change from baseline in ALSAQ40 to Week 24
- Change from baseline in body weight score at Weeks 4, 8, 12, 24, 36, and 48
- CAFS score at Weeks 24
- King's ALS Clinical Stage derived from ALSFRS-R score and death

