8.4.2. Efficacy Measures

8.4.2.1. Combined Assessment of Function and Survival Score (CAFS)

CAFS ranks patients' clinical outcomes based on survival time and change in the ALSFRS-R score¹⁰.

CAFS Scoring:

To calculate a patient's CAFS, each patient is compared individually to all other patients in the study. The summary score for each patient is the sum of the comparisons (1, 0, 1) against all other patients (Figure 2). For each pairwise comparison of patients, the patient who fares better earns a point, and the one who fares worse loses a point. In the case of a tie, no points are added or subtracted. If both participants die, the one surviving longer fared better; if only one survives then that patient fared better; and if both participants survive, the one with the smaller decline in ALSFRS-R from baseline to week 48 fared better. If a participant discontinues early or ALSFRS-R at week 48 are missing, the participant will be treated as alive at week 48 and the ALSFRS-R at week 48 will be imputed missing using multiple imputation under missing mechanism assumption.

CAFS Ranking:

Next, patients' summary scores are ranked (Figure 3). In general, the ranking has the following characteristics:

- (1) The first patient who dies will have the lowest score and is ranked the lowest;
- (2) the last to die is ranked above all others who die;

- (3) Among survivors, the patient with the greatest decline in ALSFRS-R is ranked just above the last patient who died;
- (4) The surviving patients with the least decline in ALSFRS-R is ranked highest.

[REDACTED]

[REDACTED]

The average rank score is then calculated for each treatment group. A higher mean rank score indicates that participants in that treatment group, on average, fared better.

Figure 2: [REDACTED]

8.4.2.2. %Slow Vital Capacity (%SVC) Change from Baseline at week 4, 8, 12, 24, 36 and 48

SVC measurements will be conducted in clinic at around the same time of day where possible with the subject in sitting upright position. Subjects should make at least 3 attempts to generate acceptable and reproducible SVC data. If subjects cannot complete all three attempts due to disease progression or other reasons, it will not be considered a protocol deviation. The best value will be selected and will be recorded in the eCRF.

8.4.2.3. ALSAQ40 Change from Baseline at week 24 and 48

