9.2.1.1. Primary Analysis

More than a few death events ($\geq 5\%$ death percentage for all randomized subjects, eg, ≥ 19 death events) were observed in the data review meeting, the primary endpoint analysis using mixed model repeated measures (MMRM) was replaced with the ranking score on CAFS score at Week 48 based on a joint rank score derived from change from baseline in ALSFRS-R score and time to death through Week 48 with analysis of covariance (ANCOVA) specified in the secondary endpoint analysis. Therefore, the primary analysis will be the CAFS analysis at week 48 using ANCOVA following multiple imputation assuming Missing At Random (MAR) for the FAS.

Statistical Analysis Plan
Protocol No. MT-1186-A02

Mitsubishi Tanabe Pharma America, Inc.

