The simulation results shows that the probability of stopping the study for futility under the alternative hypothesis on delta of 2.6 and the null hypothesis on delta of 0 is 4.5% and 67.1% respectively.

Given the IA results for comparing oral edaravone 105mg daily versus oral edaravone 105 mg oral on/off (details will be specified in a separate SAP), the conditional power to reach statistical significance at the end of the study will be computed. This conditional power will assume that the delta for unobserved data will follow 2.6 units as assumed in the design stage. The computed conditional power will be compared to the above specified stopping rule.

Recommended Decision Making Process

- If the calculated conditional power will meet this futility rule (i.e. Conditional Power < 42.5%), then, Independent Data Monitoring Committee (IDMC) will recommend to “Halt the study due to futility on the primary endpoint”.
- The IDMC will also perform IA for secondary efficacy endpoint, other efficacy endpoints, and safety endpoints in an exploratory manner.
- The IDMC will also look at ALSFRS data for the ongoing patients
- The IDMC will review all endpoints result and recommend the following
 - Halt the study if futility is observed or
 - Continue the study until completion.

As the above IA does not allow the early stopping of the study for proven efficacy, there will be no impact on the type I error for the final analysis. That is, the Sponsor will maintain the type I error for final analysis on 1-sided 0.025.

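### Does SAP 4.2 need a power figure for CAFS now that CAFS has replaced ALSFRS-R change as the primary endpoint?

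*SAP*

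**What the plan says.** SAP 3.2.1 applies a switch already written into the protocol: "It was confirmed that the threshold of 19 death cases was crossed in the blinded data review meeting". SAP 3.3.1 then states that "The primary efficacy endpoint is CAFS score at Week 48", and SAP 9.2.1.1 that "the primary analysis will be the CAFS analysis at week 48 using ANCOVA following multiple imputation". The former primary variable is listed in SAP 3.3.3 among the other secondary endpoints: "Change from baseline in ALS Functional Rating Scale-Revised (ALSFRS-R) score at Weeks 4, 8, 12, 24, 36, and 48".

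SAP 4.2 makes two power statements.

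- A t-test on ALSFRS-R change to Week 48, with 30% dropout: the sample size "will provide 85.5% power to detect an effect size of 0.37".
- A log-rank test on time to death, tracheostomy or permanent ventilation: 78% power at a hazard ratio of 0.3, "assuming 90% survival rate at Week 48 for the control group".

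SAP 4.2, SAP Appendix 1, protocol 17.2 and protocol Appendix 6 contain no effect size, mortality assumption or power for CAFS. The simulated operating characteristics in the two appendices also concern the ALSFRS-R difference only.

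**The concern.** A power section normally speaks to the primary test, and this one does not. A reader in a hurry could carry 85.5% over to CAFS, where it does not belong.

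CAFS places every death below every survivor. For missing scores, SAP 8.4.2.1 says: "If a participant discontinues early or ALSFRS-R at week 48 are missing, the participant will be treated as alive at week 48", with the score then multiply imputed. Deaths that fall equally in the two arms add ranks that carry no treatment difference, which dilutes a functional effect. Deaths that favour one arm move the result directly. Power can therefore lie well below or well above 85.5%. If the true figure were low, a non-significant primary result would be open to argument about whether the trial could have succeeded.

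Appendix 1 has a related leftover. Its futility rule is computed on a 2.6-unit ALSFRS-R difference, yet the recommendation reads "Halt the study due to futility on the primary endpoint", which in the current SAP would mean CAFS.

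**Working it through.** **1. The stated 85.5%.** Inputs from SAP 4.2 and Appendix 1: 190 per arm, 30% dropout, difference 2.6, SD 7, two-sided 5%.

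- Completers per arm: 190 × 0.70 = 133.
- Noncentrality: (2.6/7) × √(133/2) = 0.3714 × 8.155 = 3.029.
- Power from the noncentral t with 264 degrees of freedom: 85.5%. The normal approximation gives 85.7%.

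The figure is right for the endpoint it names.

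**2. The stated 78%.** Inputs: 90% control survival, hazard ratio 0.3.

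- Test-arm survival: 0.9^0.3 = 0.969.
- Expected events: 190 × 0.10 + 190 × 0.031 = 19 + 5.9 = 24.9.
- Freedman: Φ(√24.9 × 0.7/1.3 − 1.96) = 76.7%. A comparison of proportions, 10% against 3.1%, gives 77.6%. Schoenfeld's formula gives 85.2%.

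The figure is approximately reproduced. It does not stand in for CAFS, because the event includes tracheostomy and ventilation, whereas CAFS uses death alone.

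**3. Cost of ranking alone.** With no deaths, the relative efficiency of ranks under normality is 3/π = 0.955. Power is Φ((2.6/7) × √(133 × 0.955/2) − 1.96) = 84%. Most of any departure from 85.5% therefore comes from deaths.

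**4. Illustrative CAFS power.** At least 19 deaths is 19/380 = 5% of the planned number. The split between arms is unknown, so death rates and death hazard ratios below are assumptions. The 2.6 points and SD 7 are kept among survivors, survival is exponential, and the test is a t-test on joint ranks without covariates. Two approaches were used:

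- **Imputation:** 190 per arm, 30% missing, 20 imputations, 3,000 trials per setting. Ranges cover deaths counted within the 30% or in addition to it. It was run without earlier-visit information, and for some settings with an assumed correlation of 0.7 between earlier visits and Week 48.
- **Simple:** 133 informative patients per arm including deaths, no imputation, 6,000 trials.

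| Deaths by Week 48 | Imputation, no earlier visits | Imputation, correlation 0.7 | Simple |
|---|---|---|---|
| None | 83–85% | not run | 83% |
| 5% in each arm | 78% | 83–84% | 75% |
| 10% in each arm | 69–74% | 75–78% | 66% |
| 10% control, HR 0.7 | 85–88% | not run | 81% |
| 10% control, HR 0.3 | 96–97% | 98% | 94% |

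With 5% pooled deaths and a hazard ratio of 0.3 (7.6% against 2.4%), imputation without earlier visits gives 94–95%. If survival were worse on daily dosing (10% control deaths, hazard ratio 1.3), the simple version gives 46%.

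**5. Sensitivity to what is not visible.** The ANCOVA covariates and the imputation model cannot be read in the public SAP. With equal 5% deaths, correlation 0.7 and covariates assumed to explain 10% of the variance, CAFS power is 85.2–85.6%, so no shortfall against 85.5%. With 5% explained it is 83%. The same earlier-visit information would also raise the ALSFRS-R comparison: the variance is 2 × 49 × (0.51/133 + 0.49/190) = 0.629, and power is Φ(2.6/√0.629 − 1.96) = 90.7%.

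**The case for a change.** The best argument for acting is that CAFS was already the named backup primary in protocol 17.1.1, so its power could have been worked out in advance. SAP 4.2 was also edited after the protocol: it attaches the 78% to a specific composite event, which protocol 17.2 does not. The SAP stays open until database lock, and a figure written down before lock would forestall later argument over a null result. The cost is a sentence and a small simulation.

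Most of that is true, and the omission is not an effect of redaction, since SAP 4.2 shows none. What it lacks is a consequence. The interpretive tools for a null CAFS result are already planned. Protocol 17.4.5.1 calls for the ALSFRS-R mixed model and a Cox model if CAFS is used. SAP 9.2.1.5.1 keeps the Week 48 ALSFRS-R estimate with its confidence interval, and SAP 9.2.1.4.5 keeps time to death. Those estimates say more about a null result than a design-stage power would.

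On the futility rule, Appendix 1 states its 2.6-unit basis openly, so the endpoint behind the 42.5% limit is not in doubt and the phrase is a clerical leftover. Recomputing conditional power on CAFS would be a larger step. It would replace that limit and need new operating characteristics. The documents do not show whether the interim had already run, and its details sit in a separate SAP that is not available here.

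**Conclusion.** No change to the plan is called for. The gap exists: the SAP states power for ALSFRS-R change and for a time-to-event composite, and none for its primary endpoint. But both stated figures are correctly labelled, 85.5% reproduces exactly, and 78% reproduces approximately. Anyone who needs the power of CAFS can simulate it from the plan's own inputs, as above.

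The answer is a range and not a shortfall. Across the unadjusted simulations it is about 66–84% if survival is equal at 5–10% deaths, and about 94–98% under a death hazard ratio of 0.3. Protocol 7.2.6 expects benefit on both progression and survival, so equal survival is not the plan's own scenario. A hazard ratio of 0.3 is a strong assumption too, and the truth may lie between. All of this depends on an unknown death split, assumed correlations, and covariates and an imputation model that cannot be seen. It does not show that the trial is underpowered.

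Writing such a table into SAP 4.2 would leave the sample size, the test and the decision rule as they are. Calling 85.5% the design-stage figure for the former primary endpoint would be tidier, but no result or conclusion turns on it.
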